Eight participating hospitals will be randomized to a staggered sequence (i.e., steps 1 to 8) of transitioning from UC to STAR group assignments using SAS Enterprise Guide v7.1 (Cary, NC). All eight hospitals will start with a control period of varying length, dependent on timing of transition to the intervention arm. Every four months, one randomly assigned hospital will cross over to initiate the STAR program and remain in the intervention arm through study completion. All patients identified as eligible using the risk model will be allocated to the study ARM that matches the admitting hospital's assignment (STAR or UC). During the intervention phase at each facility (i.e., after transition from UC to STAR), the navigator will receive the list of admitted, high risk patients via secure email.

Study Procedures

Patient identification: Each morning, the list of eligible, high-risk patients is automatically securely transmitted to the study database within REDCap and the study PIs are notified of completed transmission. The list of eligible, high risk patients at hospitals allocated to receive the STAR program (based on randomly assigned months) will also be automatically emailed via secure transmission to the STAR navigators.

Initial contact with the STAR program: After the patient list is generated, the STAR navigator will contact the care team (e.g., bedside nurse, hospitalist) to obtain permission to discuss the STAR program with patients assigned to STAR. At any time, the hospitalist, bedside nurse, or

patient may decline for the patient to participate in the STAR program or any components of usual care.

Summary of STAR services duration: The STAR navigator will provide telephone- and EHR-based support within the hospitalization and to patients across all discharge settings with remote monitoring at specified intervals following hospital discharge. Within 48 hours of discharge, patients allocated to STAR will have their first post-discharge follow-up. They will continue to receive STAR directed services for 90 days following their discharge. Subsequently, they will be transitioned back to the next appropriate care location.

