Irrespective of discharge location (e.g., home versus skilled nursing facility), the STAR navigator will provide monitoring through phone contact with patient, caregiver, or provider (as appropriate for post-acute care location) at <48 hours, 72-96 hours, and 7-10 days post-discharge. These touchpoints will include medication reconciliation, infection and respiratory symptom monitoring, vitals and weight checks, and confirmation that the patient can make scheduled outpatient appointments. Concerns identified through proactive monitoring will prompt a primary care provider contact for follow-up. If the primary care provider cannot be reached after one attempt, the navigator will contact the hospitalist back-up provider. Following the immediate post-acute interval, the STAR navigator will maintain weekly telehealth touchpoints with patients who remain at high-risk for poor outcome (i.e., any previous positive screen, high-risk comorbid condition [e.g., chronic lung disease, heart failure], or low health literacy) and every third week touchpoints with patients considered low-risk after the immediate post-acute interval. These 90-day post-acute touchpoints will include infection and respiratory symptom check, vitals and weight monitoring, and consideration for repeat outpatient provider visit. Identified concerns will prompt attempts to contact the primary care provider followed by hospitalist back-up provider. The STAR support service will complete 90 days post hospital discharge.

Statistical Analysis

Sample Size Determination: This study is designed to detect a 20% relative reduction in composite 90-day mortality and hospital readmission. The usual care group is indicated to have

roughly 40% combined 90-day mortality and readmission rate. With a total sample size of 4392 patients enrolled over 36 unit-months, we will have 90% power ($\alpha=0.05$) to detect a 20% relative reduction in composite 90-day mortality and hospital readmission.

Statistical Methods

Aim 1: Evaluate the effectiveness of an innovative, virtual nurse navigator implementation strategy to improve post-sepsis care.

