All primary and secondary analyses will follow intention to treat approach, such that all patients meeting identical criteria and randomized will be analyzed, regardless of adherence to intervention assignment. This real-world approach will assess intervention effectiveness while limiting selection biases associated with adherence. We will compare the two groups (STAR versus usual care) at baseline for age, sex, race, and comorbidities to assess for balance inferred randomization. The primary outcome is the composite of hospital readmission and mortality at 90 days post hospital discharge. Because hospitals are randomized to STAR in a staggered sequence and the outcome varies at the patient level, we will use a generalized linear mixed-effects model to compare the composite 90-day mortality and readmission primary outcome measure between the intervention conditions, adjusting for clustering effects across multiple levels (e.g., admitting hospital, implementation timing) to include hierarchical data structures. The intervention fixed-effect coefficient will compare STAR versus UC conditions (i.e., UC as reference). We will evaluate covariates for patient (e.g., sex, race, comorbidities, length of stay, discharge disposition [skilled nursing facility, rehabilitation, home]) and organizational factors (e.g., admitting hospital, guideline adherence, urban versus rural setting, implementation timing) to identify any potential differences between study arms. We will include covariates in model if unbalanced between STAR and UC groups. We will also evaluate effect

modification by conducting analyses stratified by these characteristics (e.g., discharge disposition) and by process measures with potential to effect outcomes (e.g., referrals).

Secondary outcomes are described below and will be assessed using the same approach. That is, we will construct generalized linear mixed-effects models, like for the primary outcome analysis, for individual assessments of secondary outcomes and process measures. We will test different distribution parameters to determine the optimal distribution family for each model and outcome variable (e.g., binomial, gamma distributions).

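### The primary stepped-wedge model does not fix calendar period as a fixed effect; the only time term, *implementation timing*, is undefined, and fitted as the clustering level the text names it leaves part of a steady drift in the STAR estimate

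*Combined protocol and SAP*

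**What the plan says.** The Randomization section sets a one-way crossover: "Every four months, one randomly assigned hospital will cross over to initiate the STAR program and remain in the intervention arm through study completion". It also says: "All eight hospitals will start with a control period of varying length, dependent on timing of transition to the intervention arm".

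Statistical Methods, Aim 1, chooses a generalized linear mixed model for the 90-day composite, "adjusting for clustering effects across multiple levels (e.g., admitting hospital, implementation timing) to include hierarchical data structures". The one fixed effect stated outright is the STAR versus usual care coefficient. *Implementation timing* occurs once more, in the list of organizational factors to be evaluated as covariates ("guideline adherence, urban versus rural setting, implementation timing"), under the rule "We will include covariates in model if unbalanced between STAR and UC groups". The term is not defined, and no other section specifies an adjustment for time.

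For the remaining endpoints: "Secondary outcomes are described below and will be assessed using the same approach". The Interim Analysis section gives no separate model. Sample Size Determination says: "With a total sample size of 4392 patients enrolled over 36 unit-months, we will have 90% power"; it gives neither an ICC nor a method.

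**The concern.** In a one-way stepped wedge, treatment is confounded with calendar time by design. Randomizing the order of the hospitals does not undo this; the model has to. The Aim 1 text can be followed in at least three ways, and they give different primary results.

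- **(a) Calendar period as a clustering level**, that is, a random period effect. This is closest to the main model sentence. It shrinks the period effects, so part of a drift stays in the STAR coefficient. If the level is nested within hospital, nearly all of it stays.
- **(b) Calendar time as a fixed covariate.** The arms are unbalanced on it by design, so the imbalance rule would bring it in and a common drift is removed.
- **(c) The hospital's assigned step**, the sense in which the Randomization section uses *timing*. It is constant within a hospital, largely duplicates the hospital term and removes essentially no drift. This is the worst case, and a weaker reading because it makes the term redundant.

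Under (a) or (c), event rates that fall over the 36 months would add to an apparent STAR benefit, and rising rates would hide part of a real one.

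**Working it through.** **Inputs from the documents.** Eight hospitals, one crossing every four months, all starting in usual care, 36 months: nine periods, with 0, 1, …, 8 hospitals on STAR. N = 4392 = 8 × 9 × 61. Planned effect 40% to 32% (8 pp), two-sided α = 0.05, 90% power.

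**Assumptions, not in the documents.** Equal cells of 61; ICC 0.02 unless stated; linear drift common to all hospitals; within-hospital correlation constant over time. Calculations use hospital-period means on the risk-difference scale, with total variance 0.36 × 0.64 per patient.

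**1. The plan's sample size.** Without clustering, 40% vs 32% needs 755 per arm, 1510 in total; 4392/1510 = 2.9, so the stated N carries a design inflation. With a random hospital intercept, power = Φ(8/SE − 1.96):

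| Model | SE at ICC 0.02 | Power at 4392 (ICC 0.01 / 0.02 / 0.05) | N for 90% power |
|---|---|---|---|
| Fixed period effects | 2.44 pp | 91.7 / 90.6 / 90.5% | 4091 / 4288 / 4318 |
| No time term | 1.64 pp | 99.8% at each | 1829 / 1888 / 1891 |

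For example, Φ(8/2.44 − 1.96) = Φ(1.32) = 90.6%. The stated N and power match a period-adjusted model.

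**2. Confounding with time.** The mean period is 3.33 for usual care and 6.67 for STAR: 3.33 periods × 4 months = 13.3 months.

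**3. Bias with no time term, or with the assigned step (c).** In a hospital with k usual-care periods, the mean usual-care period is (k + 1)/2 and the mean STAR period is (k + 10)/2. The difference is 4.5 periods whatever k is. A purely within-hospital comparison therefore carries 4.5 pp of bias per 1 pp of drift per period. Generalized least squares, β = (Z′V⁻¹Z)⁻¹Z′V⁻¹y with y set to the drift, gives 4.50 pp with the step as covariate and 4.27 / 4.37 / 4.45 pp with no time term (ICC 0.01 / 0.02 / 0.05). Type I error is Φ(−1.96 + b/SE) + Φ(−1.96 − b/SE). At 0.5 pp drift under (c), b = 2.25 and SE is about 1.67, which gives 27%.

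**4. Bias with a random period effect (a).** This was simulated with REML variances (runs of 400 and 1500 trials). At 0.5 pp drift the period variance was estimated as about zero in 48–54% of trials, so those fits removed almost no drift.

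**5. Results with a true STAR effect of zero.**

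| Drift per period | (a) false effect | (a) type I error | (b) fixed period | (c) or no time term: type I error |
|---|---|---|---|---|
| 0.1 pp | 0.4 pp | 5–6% | 0 pp, 5% | 5.8% |
| 0.25 pp | 1.0 pp | 7–10% | 0 pp, 5% | 10% |
| 0.5 pp | 1.9–2.0 pp | 21–23% | 0 pp, 5% | 27% |
| 1 pp | 3.3 pp | 48–51% | 0 pp, 5% | 76% |

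A drift of 0.5 pp per period is 8 × 0.5 = 4 pp from the first period to the last. Setting the period variance to that of the drift, instead of estimating it, gives milder figures for (a): about 1.85–1.88 pp and 16–18% at 0.5 pp. A separate set of 400 simulated trials at ICC 0.01 gave 1.9 pp and 22% for the crossed random period at that drift, and 2.1 pp and 26% for a level nested in hospital.

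**6. Interim look.** With even accrual, n = 2196 is reached at 4.5 periods: 488 STAR patients and 1708 usual-care patients, 4.8 months apart on average. Even with no time term, 0.5 pp drift gives a bias of 1.0 pp (SE 3.13 pp) and a 0.16% chance of p < 0.001. The harm there is small.

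**The case against.** Time is not absent from the plan. The model sentence starts from the staggered randomization and names a timing term, and if that term means calendar time, the imbalance rule admits it and the problem disappears. The sample size also points to period adjustment having been intended. These points stand, and they make this a defect of specification. But that route requires one meaning of an undefined term to be chosen, the covariate list to be preferred to the clustering sentence, and a balance check with no stated criterion to admit it. The baseline comparison that the section does specify covers age, sex, race and comorbidities, not time.

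The harm is conditional. No drift, ICC or hospital sizes are given, and a very small drift does little. The largest figures come from 1 pp per period, which is 8 pp over the trial and as large as the planned effect. At that drift, fixing the period variance at that of the drift lowers the bias under (a) to about 2.6 pp and the type I error to about 26%. The figures also come from a linear model for cell means, not the binomial mixed model. All of this stands.

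Not every drift causes bias. With equal cells, a drift symmetric about mid-trial, such as a rise and matching fall, gives none even with no time term. That is correct; the figures above apply to a linear drift.

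The sample size inference is limited, since no ICC or method is stated. Taking 0.36 × 0.64 as residual instead of total variance gives 89.0% power at ICC 0.05, not 90.5%. The contrast with a model without time survives.

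**Conclusion.** The concern holds and should be fixed. The plan does not specify calendar period as a fixed effect, and *implementation timing* can be read in ways that give different primary results. On the reading closest to the main sentence, a linear drift of 0.5 pp per period leaves a false effect of nearly a quarter of the planned 8 pp, with type I error of about 16–23% in place of 5%. With calendar time as a fixed covariate there is no such problem. Confidence is high on the missing specification. The size of the harm rests on the assumed linear drift, equal cells and ICC of 0.02. The ambiguity carries over to the secondary outcomes, and formally to the interim analysis, where it matters little.

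**What to change.** State that calendar period is a fixed effect that is always included, together with the STAR fixed effect and a random hospital intercept, in the primary, secondary and interim models. Define *implementation timing*, and remove it from the covariates whose inclusion depends on observed balance. A hospital-by-period random effect is a reasonable sensitivity analysis.

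Nine categorical four-month periods are the safer form. With equal cells, a linear calendar term gives the same SE and also zero bias from linear drift. With assumed hospital sizes of 0.4 to 1.9 relative and a sudden 4 pp change, the linear term leaves −0.8 to +0.9 pp and categorical periods leave none, at a mean SE of 2.48 against 2.45 pp.

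**Cost.** If period adjustment was intended, the change is wording only. Against a model with no time term, the SE rises from about 1.64 to 2.44 pp at ICC 0.02. Power at 4392 is then 90.5–91.7% for ICC 0.01–0.05 if within-hospital correlation is constant over time. It is lower if the correlation decays: 84.6% at ICC 0.02 with a cluster autocorrelation of 0.8. The SAP should therefore also state the ICC and the correlation structure behind the stated 90%.

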We do not anticipate substantial missing data because all outcomes are routinely collected variables and utilization is broadly captured within the large integrated system. While utilization may occur outside of CHS, this is not expected to be a major limitation because of CHS market share and accessibility. Specifically, CHS operates three large hospitals in Mecklenburg County, the only acute care hospitals in Anson, Burke, Cleveland, Lincoln, Stanly, and Union counties, where most of this study will be conducted, and more than 40 hospitals in the region overall. Additionally, any utilization that occurs outside the system is anticipated to be non-differentially distributed between groups and thus impact treatment groups equally. Further, internal data indicates nearly 75% of high-risk patients are Medicare-insured and have complete healthcare claims within and outside CHS facilities captured through participation in the ACO managed by CHS. We will leverage this data for subgroup analyses and to explore missing data patterns that can be adjusted using pattern-mixture methods in sensitivity analyses.

All hypothesis tests will be two sided and data will be analyzed using SAS Enterprise Guide v7.1 (Cary, NC) or R v3.5 (Vienna, Austria).

Interim Analysis

Interim analyses will be conducted when 50% of enrollment targets are met and 90-day patient outcomes are obtained. All interim analyses will be presented to the Data and Safety Monitoring Board (a Steering Committee representative, an independent clinician investigator, and an independent biostatistician), who will make a recommendation on continuing the trial as planned or modified. The following analyses will be conducted by the study statistician and provided to the Data and Safety Monitoring Board:

1. Sample size re-estimation

a. Drop-out rate for STAR: We define the drop-out rate for the STAR program to be the rate of nonadherence to the intervention. Non-adherence is defined by those patients who declined, were discharged before contact by STAR staff, and were not able to be contacted after hospital discharge. The population is defined as all patients who were deemed eligible and identified as high risk for readmission or mortality. We propose to assess the drop-out rate in the STAR intervention arm when half of patients have 90-day follow up information available (n=2196). At that time, we will re-estimate the sample size needed for the study using drop-out rates.

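### Effect modification is to be evaluated by stratified analyses alone, with no planned estimate or test of how the STAR effect differs between strata

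*Combined protocol and SAP*

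**What the plan says.** Statistical Methods, Aim 1, describes a generalized linear mixed-effects model for the primary outcome with a single treatment term: "The intervention fixed-effect coefficient will compare STAR versus UC conditions (i.e., UC as reference". The same paragraph lists patient and organizational factors, one of which is "discharge disposition [skilled nursing facility, rehabilitation, home". It then says that the trial will evaluate effect "modification by conducting analyses stratified by these characteristics (e.g., discharge disposition", "and by process measures with potential to effect outcomes (e.g., referrals".

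That is everything the plan offers on effect modification for Aim 1. No STAR-by-characteristic term, heterogeneity test or contrast between strata appears there or anywhere else. The Subgroup Analyses paragraph under Aim 2 adds more subgroups and also gives no contrast. Later in the Aim 1 methods, group comparisons are to be shown as odds ratios with 95% confidence intervals, and "All hypothesis tests will be two sided". How results from different strata are to be compared is not stated.

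**The concern.** The null hypothesis of an effect-modification question is that the STAR effect is the same in every stratum. A model refitted within one stratum addresses a different null, that STAR has no effect in that stratum. The planned analyses therefore stop short of the quantity they are meant to evaluate. This is true even for characteristics fixed before admission, such as sex or comorbidity.

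What is at stake is how the stratum results will be read. Each stratum holds only part of a sample sized for the overall comparison. With a uniform effect, one stratum can easily reach significance while another does not, and a reader could take that as a sign that STAR works in some patients only. Nothing in the plan guards against this.

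**Working it through.** **Inputs from the documents.** Sample Size Determination: usual-care event rate 40%, 20% relative reduction (0.40 to 0.32), alpha 0.05, and "With a total sample size of 4392 patients enrolled over 36 unit-months, we will have 90% power". Tests are two-sided. Randomization: eight hospitals, one crossing over every four months. Over 36 months this implies nine periods, so 8 × 9 = 72 hospital-periods and 4392/72 = 61 patients in each.

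**Assumed, because the documents do not give them.** Intracluster correlation (ICC), equal hospital volumes and stratum shares.

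**Step 1: the plan's own figure.** The formula for individually randomised proportions gives 755 per arm, 1510 in total, so 4392 carries a design effect of 4392/1510 = 2.9. A stepped-wedge model with random hospital and fixed period effects gives power of 91.7%, 90.6%, 90.4%, 90.5% and 91.5% at ICCs of 0.01, 0.02, 0.03, 0.05 and 0.10. The stated 90% is thus reproduced within 2 points over that range. At ICC 0.005 power is 93.5%, and at ICC 0 it is 98.8%.

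**Step 2: how often strata disagree on significance when the effect is uniform.** At 90% power the expected overall z is 1.96 + 1.28 = 3.24. A stratum with share f has expected z = 3.24 × √f and power p = Φ(3.24√f − 1.96). The probability that strata disagree is 1 − ∏p − ∏(1 − p).

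| Strata | Power in each | Disagree |
|---|---|---|
| 50/50 | 0.63, 0.63 | 2 × 0.63 × 0.37 = 0.47 |
| 70/30 | 0.77, 0.43 | 0.54 |
| 80/20 | 0.83, 0.30 | 0.63 |
| Three equal | 0.46 each | 0.75 |

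A formal test of the difference rejects in 5.0% of trials, for two strata and for three.

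**Step 3: sensitivity, two equal strata.** True uniform reduction of 10%: 33%. 15%: 48%. 25%: 30%. 30%: 13%. No effect: about 5% counting STAR-favouring significance only, about 10% counting either direction. Applying the stepped-wedge model directly gives 43% to 46% for ICCs of 0.01 to 0.10, and 26% at ICC 0.

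**Step 4: simulation of the planned layout.** 61 patients per hospital-period, hospital SD 0.18 on the logit scale, a binary baseline characteristic, and logistic fits with fixed hospital and period effects as a stand-in for the mixed model. Overall power was 88% to 89%. With a uniform risk ratio (RR) of 0.80, 3,000 trials per scenario gave disagreement in 47%, 55% and 63% for 50/50, 30/70 and 20/80 splits.

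**Step 5: two ways to make the formal contrast.** The first is one model with shared hospital and period effects plus a STAR-by-characteristic term. The second is the difference of the separately fitted stratum coefficients. Rejection rates:

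| Scenario | Shared effects | Difference of separate fits |
|---|---|---|
| Uniform RR 0.80, no differing trends | 5–6% | 5% |
| Uniform RR 0.80, characteristic-specific trend, OR 1.5 over the trial | 17–23% | 4–7% |
| Uniform RR 0.80, characteristic-by-hospital SD 0.3 (logit) | 13% | 4–7% |
| Uniform RR 0.80, characteristic doubles baseline odds | 15% | 4–7% |
| RR 0.90 versus 0.70, equal strata | about 82% | 37–39% |
| RR 1.0 versus 0.7, equal strata | 99% | 70% |

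The trend, hospital SD and prognostic strength are assumptions. A hand check agrees with the 37–39%. Effects of 0.5 and 1.5 times the average in equal strata give an expected z for the difference of 3.24/(√2 × √2) = 1.62, and Φ(1.62 − 1.96) = 0.37.

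**Step 6: scale.** At a baseline risk of 0.40, RR 0.80 is an odds ratio of (0.32/0.68)/(0.40/0.60) = 0.71. Doubling the baseline odds gives a risk of 0.571. RR 0.80 then gives 0.457, and an odds ratio of (0.457/0.543)/(0.571/0.429) = 0.63. One risk ratio is therefore two odds ratios when the characteristic is prognostic. Either contrast on the odds-ratio scale is then looking at a real difference. The lower rate for separate fits in that row reflects lower power and does not solve the scale problem.

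**The case against.** The strongest reply is that the plan contains no rule that significance in one stratum and not another means effect modification. Stratum-specific odds ratios with confidence intervals can be compared, and estimating within strata and then comparing is a recognised approach. When the separately fitted coefficients are compared formally, the false-positive rate is about 5%, the same as for an interaction test. All of this stands. A reader might infer that the plan will produce false effect modification about half the time, or that stratifying itself inflates error. The documents support neither. The 47% depends on an assumed reading, on two roughly equal strata, and on a true effect and power near the design values.

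A second reply is that a shared-effects interaction model is no safe replacement. This also stands. STAR exposure rises with calendar time and enrolment runs from July 2020 through June 2023, so a trend that differs by characteristic can pass for an interaction. Its large power advantage exists only if its assumptions hold.

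A third reply is that the only named examples in the sentence, discharge disposition and referrals, can arise after allocation. A formal contrast does not cure that; it is a separate issue. Nor does any passage tie dissemination of STAR to subgroup significance, so harm through wrong targeting is a possibility and not a stated consequence.

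What the replies leave untouched is the gap itself: a stated aim to evaluate effect modification, with no between-stratum quantity planned.

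**Conclusion.** The point holds as a gap in the method. The plan sets out to evaluate effect modification and names only within-stratum analyses, which do not estimate or test the difference in STAR effect.

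If discordant significance were used as the criterion, the false-signal rate under a uniform 20% reduction and 90% overall power would be about 47% for two equal strata, 54% to 63% for 70/30 to 80/20 splits and about 75% for three equal strata, against about 5% for a formal test. These figures rest on that reading, on the plan's stated power and on independent strata. They fall when the true effect or the power differs enough from the design. The matter concerns supportive analyses only; the primary estimate and its error control are not touched. It should be corrected, at small cost.

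**What to change.** In Statistical Methods, Aim 1, replace the sentence on effect modification with the following provisions.

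- For each baseline characteristic, base any statement about effect modification on a formal STAR-by-characteristic contrast with its 95% confidence interval and p-value (a joint test where there are three or more levels). Report stratum-specific STAR effects as description only, and say that significance in one stratum and not another is not evidence of modification.
- In the main version, let the characteristic interact with calendar period and with hospital as well as with STAR; equivalently, use the difference of the stratum-specific coefficients.
- Report the model with shared hospital and period effects as a more powerful secondary fit, valid only if trends and hospital effects do not differ by the characteristic.
- State the scale: odds ratio, or also risk ratio or risk difference.

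The cost is SAP wording and some model terms, with no new data or patients. The downside is limited power for the main contrast (about 37% to 39% for RR 0.90 versus 0.70 in equal strata, against about 82% for the shared-effects fit if its assumptions hold), so fewer subgroup differences will be claimed. Stratifying on post-allocation factors such as discharge disposition or referrals needs its own answer.
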